#### Power

Since the project's results can have immediate effects on how LP is performed both nationally and internationally, we have chosen to perform an interim analysis after 2 years of study duration (1/1 2016). If clear results appear already then, the project will be interrupted. If the study runs for the full 3 years, it is estimated to include approximately n = 900 patients. These will be randomized so that approximately n = 150 ends up within each needle / stylet category (n = 300 / needle). In power calculations we assume an alpha = 0.05, power = 80%, a chi-2 test to show differences between the groups, and 900 participants. With regards to the difference between needles, it has previously been shown that LP with a non-cutting needle (22G) gave a PLPH incidence of 12.2%, compared to cutting (22G) 24.4%. To detect this difference, power calculations suggest n = 157 individuals in each group (we will have n = 300 after 3 years, n = 200 after 2 years). The difference in PLPH frequency between reinserting the stylet or not was 5% vs. 16% with a non-cutting 21G needle. Such a difference would require n = 121 patients in each group (we will have n = 450 after 3 years, n = 300 after 2 years). Size: The frequency PLPH with 24–27G needle is 5–12%, and for needles in sizes 20–22G 20–40%. To detect the smallest possible difference (20% vs. 12%) we would need n = 329 patients (we will have n = 300 after 3 years, n = 200 after 2 years).

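### The 2-year stop on 'clear results' has no numerical boundary, no matching final level and no named comparison, so the 0.05 level is not guaranteed and it is open which comparisons an early stop would cut short

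*Combined protocol and SAP*

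**What the plan says.** All the relevant text is in the Power section. The sponsor writes "we have chosen to perform an interim analysis after 2 years of study duration (1/1 2016"), giving as the reason that the results may change practice at once. The next sentence is the whole stopping rule: "If clear results appear already then, the project will be interrupted". What stops is the project, not a single comparison.

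The only significance level appears in the sample size statement: "In power calculations we assume an alpha = 0.05, power = 80%, a chi-2 test to show differences between the groups, and 900 participants". Three comparisons are then sized separately:

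- **Needle type:** 12.2% vs 24.4%, from 22G needles; 157 per group needed; 200 available at 2 years, 300 at 3 years.
- **Stylet:** "The difference in PLPH frequency between reinserting the stylet or not was 5% vs. 16% with a non-cutting 21G needle"; 121 per group needed; 300 available at 2 years, 450 at 3 years.
- **Needle size:** 20% vs 12%, for which "we would need n = 329 patients (we will have n = 300 after 3 years, n = 200 after 2 years").

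No other section adds a boundary, a final level or a governing comparison.

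**The concern.** This is an efficacy look that can end the trial, and its rule would have to be given a meaning after the comparative data have been seen. That leaves two things open.

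The first is the error rate. A test at 0.05 after 3 years, preceded by an undefined chance to declare success at 2 years, has an overall error that depends on a number the plan does not give.

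The second is the scope of the stop. Three questions with different expected effects share one trial. If a clear answer to one ends recruitment for all, the others are analysed at two-thirds of their planned size.

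That could matter for a decision the protocol describes. Purpose and method says that if headache incidence with the cutting 25G needle is already low, and the atraumatic needle of the same size does not lower it significantly, the cutting needle may be a reasonable choice on cost grounds. A type comparison cut short could contribute to that conclusion.

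**Working it through.** **1. Reproduce the stated sample sizes.** Inputs: the rates above, alpha 0.05 (sidedness is not stated), 80% power, chi-square test, equal groups. With p̄ the mean of the two rates,

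n = [1.960·√(2p̄(1−p̄)) + 0.842·√(p1(1−p1) + p2(1−p2))]² / (p1−p2)².

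| Comparison | Rates | Stated n | Two-sided | One-sided | Two-sided, continuity-corrected |
|---|---|---|---|---|---|
| Type | 12.2% vs 24.4% | 157 | 157 | 124 | 173 |
| Stylet | 5% vs 16% | 121 | 121 | 95 | 139 |
| Size | 12% vs 20% | 329 | 329 | 259 | 354 |

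The plan's figures are therefore two-sided 0.05 with a single analysis. None allows for the interim look.

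**2. Information at the look.** 200/300 = 300/450 = 2/3 for every comparison.

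**3. Type I error over the two looks.** Under the null, the interim and final statistics are approximately bivariate normal with correlation √(2/3) = 0.816. Overall error = 1 − P(|Z1| < c1 and |Z2| < c2). With c2 = 1.960 (final test at 0.05):

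| Assumed meaning of 'clear' | c1 | Overall error per comparison |
|---|---|---|
| p<0.05 | 1.960 | 0.0770 |
| p<0.01 | 2.576 | 0.0526 |
| p<0.001 | 3.291 | 0.0501 |

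All three meanings are assumptions, because the documents give none.

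**4. Boundaries that hold 0.05 at fraction 2/3.**

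- p<0.001 at the interim, then 0.0499 at the end.
- Lan-DeMets O'Brien-Fleming-type spending applied to the whole two-sided 0.05. The interim level is 2[1 − Φ(1.960/√(2/3))] = 2[1 − Φ(2.400)] = 0.0164. Solving for the final level gives 0.0439.

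**5. Power at the 2-year and 3-year sizes.** Power = Φ{[|p1−p2|·√n − 1.960·√(2p̄(1−p̄))] / √(p1(1−p1) + p2(1−p2))}, tested at 0.05. For size at 20% vs 12% with n = 200: (0.08 × 14.142 − 1.960 × 0.5185)/0.5154 = 0.22, so power is 0.588. With n = 300 the value is 0.72, so power is 0.763.

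| Comparison | Rates | Source of rates | 2 years | 3 years |
|---|---|---|---|---|
| Size | 20% vs 12% | plan | 59% | 76% |
| Size | 12.2% vs 6% | plan's non-cutting 22G rate; 6% assumed | 58% | 75% |
| Type | 24.4% vs 12.2% | plan (22G) | 89% | 97% |
| Type | 12% vs 6% | assumed for 25G | 55% | 73% |
| Stylet | 16% vs 5% | plan (21G) | 99% | above 99.9% |

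The assumed rows are there because the planning rates come from other needles. The trial compares type at 25G, and the plan puts 24–27G needles at 5–12%. Both needles in the size comparison are atraumatic, and the plan's own figure for a non-cutting 22G needle is 12.2%, not 20%. The size result varies with the assumed 25G rate: 12.2% vs 5% gives 73% against 88%, and 12.2% vs 8.5% gives 23% against 32%.

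**6. Would a strict boundary alone protect the other comparisons?** At 5% vs 16% the stylet comparison reaches p<0.001 at the interim in about 87% of trials. If that ended the whole project, simulation (1,000,000 trials, stylet treated as independent of the needle comparisons) gives size power at 20% vs 12% of 62%, against 77% if the trial runs on. With a weaker stylet effect (assumed 12% vs 6%), p<0.001 is reached in about 23% of trials and size power is 73% against 77%. A strict level therefore settles the error rate but not the scope of the stop.

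**The case against.** The strongest reply is that a result clear enough to halt a trial and change national practice is naturally read as something much stricter than p<0.05, and at p<0.001 the inflation is negligible. That is fair. A reader might infer that the trial's error rate is 0.077. The documents do not support that, because they never say 0.05 is used at the interim. The supportable range is 0.050 to 0.077. What stands is that nothing commits the team to the strict end before the data are seen.

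A reader might also infer that one clear comparison will end the others. The sentence refers to results in the plural and could mean that all the main questions must be answered, in which case the loss in step 6 does not arise. The text does not settle it.

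On the plan's own rates, type and stylet already exceed their required numbers at 2 years (200 against 157, 300 against 121). Only size falls short, and it is short at 3 years too (300 against 329). The plan discloses that shortfall, and the look does not cause it. The further drop from 76% to 59% would be caused by an early stop.

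Finally, it would be too strong to say that the protocol adopts the cutting needle whenever the type test is not significant. Purpose and method also requires a low incidence with that needle, and says only that the choice may be reasonable.

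**Conclusion.** The concern holds as an omission that should be repaired before the interim analysis: 'clear' is undefined, the final level does not allow for the look, and the governing comparison is not named. Following the plan as written does not guarantee 0.05 per comparison. The error lies between 0.050 and 0.077 for interim levels from p<0.001 to p<0.05, assuming two-sided tests, a final test at 0.05 and an information fraction of 2/3. These error figures do not depend on any headache rate.

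The power loss is conditional. It arises only if one comparison can end the project. On the plan's rates it falls mainly on size (59% against 76%), while type and stylet stay above 80% at 2 years. At lower type rates, assumed at 12% vs 6%, type would also be affected (55% against 73%). All the power figures rest on rates from other needles or on stated assumptions, so they show the scale of the loss and do not predict this trial's power.

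**What to change.** Before any interim data are seen, amend the Power section to:

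- replace 'clear results' with a numerical boundary and matching final level for each comparison, for example p<0.001 at the interim and 0.0499 at the end (leaving 0.05 at the end gives 0.0501), or a two-sided Lan-DeMets O'Brien-Fleming-type boundary of 0.0164 then 0.0439;
- name the comparison or comparisons that govern stopping, and state that the project as a whole stops only when those have crossed, so that one clear comparison does not by itself end the others;
- say what happens to randomisation for a comparison that has crossed while the others continue.

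The cost is a few sentences of wording. Early stopping becomes less likely: at p<0.001 the interim is crossed by type in about 45% of trials at the plan's 22G rates (about 10% at an assumed 12% vs 6%) and by size in about 13% at 20% vs 12%. Some comparisons may also continue while the result of another is already known. The effect on final power is small: for size at 20% vs 12%, with stylet randomisation continuing, it is about 76.7% with p<0.001 then 0.05 (0.0499 differs negligibly) and 75.7% with 0.0164 then 0.0439.

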## **Background**

Lumbar puncture (LP) with spinal fluid analysis (CSF analysis) is a common procedure at neurological clinics. At the neurology clinic in Umeå, about 250-300 LP is carried out every year at a specialized LP lab, and an additional 50 LP at the ward (usually on on-call time when the LP-lab is closed). Common indications include suspected bleeding, infection, inflammation, neurodegenerative processes and CSF pressure measurement.

A relatively common complication after LP is post-LP headache (PLPH). This complication occurs in between 20 and 30% of all who have undergone an LP. It is characterized by being positional, i.e. worsens in standing (within 15 minutes after standing up) and improves/completely resolves upon lying down (within 15 minutes after lying down). PLPH occurs within 5 days of LP, and disappears within 1 week of occurrence. The headache is often associated with one of the following: neck stiffness, tinnitus, mildly impaired hearing, photosensitivity, nausea. (See International Headache Society's definition: <http://ihs-headache.org>). It is not known today why PLPH occurs, but a commonly adopted theory is that there is a leakage of CSF through the hole that has been made, which thus causes low hydrostatic pressure in the central nervous system (CNS). This either causes a painful vasodilation of veins within the CNS or traction of the pain-sensitive meninges, or both. Recommendations for relieving PLPH usually include bed rest (when PLPH has occurred - there is no evidence that bed rest prevents the occurrence of PLPH), fluid intake, caffeine intake and common analgesics. As a curative treatment in difficult-to-treat cases, one may administer a bloodpatch, which means that 15-20 ml of autologous blood is injected into the epidural space, preferably at the same level as the original LP. This is believed to have the effect of both clogging the leaking hole (platelet plug), and exerting a pressure on the spinal cavity, which increases the pressure in the CNS and thus reduces the effect of the lost amount of CSF.

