ensure an even distribution of these baseline characteristics across each needle/stylet category. People who undergo LP at the neurological clinic, NUS during a 3-year period (from January 1, 2014 - December 31, 2016), and who are judged to be able to answer the follow-up questions, will be asked about participation. Data is collected during the LP itself, and at a follow-up telephone call by a blinded nurse at the neurology outpatient clinic 5 days after LP, repeated after 5 days if still having PLPH. The more exploratory parameters that are investigated are whether the opening CSF pressure is important for the risk of PLPH, and whether the volume of CSF drawn is of importance for the risk of PLPH. In addition to this, data on the intensity of the headache as well as possible sick leave are registered. As a welcome side effect of the study, we also hope that the use of small non-cutting needles increases in the clinic with reduced occurrence of PLPH as a result. A challenge lies in instructing medical student who perform many of our LPs in the use of these needles, and this parameter is also interesting to study. One of the strengths of the study is that the setting is "real life" with several different operators, supervision of medical students and an unselected patient material. We believe this may increase the external validity of the study results.

In parallel with the study, an anonymous, web-based questionnaire will be distributed via e-mail to the members of the Swedish Neurologist Association. In this questionnaire, the respondent's current approach to routine lumbar puncture (needle type, size, stylet reinsertion or not, and knowledge of AAN's guidelines) is requested. These data, together with the study results, will form the basis for health-economic calculations on various lumbar puncture strategies in Sweden, and will be used primarily in connection with the study results being reported in the form of a debate entry in e.g. Läkartidningen.

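### The planned 900 patients equal 86–100% of all lumbar punctures the clinic reports, leaving almost no room for non-participation or loss; the cost falls mainly on the needle-size contrast (76% power at best under the plan's 900)

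*Combined protocol and SAP*

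**What the plan says.** The Power section assumes alpha 0.05, 80% power, "a chi-2 test to show differences between the groups, and 900 participants". It expects that number from the full recruitment period: "If the study runs for the full 3 years, it is estimated to include approximately n = 900 patients". From it come 300 patients per needle and 450 per stylet option after 3 years, and 200 and 300 after 2 years. The n needed per group is given as 157 for needle type (24.4% vs 12.2%), 121 for stylet (16% vs 5%) and 329 for needle size (20% vs 12%). For size the plan prints need and supply together: "we would need n = 329 patients (we will have n = 300 after 3 years, n = 200 after 2 years". It does not state the power that results.

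The Background gives the clinic's volume: "about 250-300 LP is carried out every year at a specialized LP lab, and an additional 50 LP at the ward". Purpose and method defines the source population and window as "People who undergo LP at the neurological clinic, NUS during a 3-year period (from January 1, 2014 - December 31, 2016", and limits the approach to those "who are judged to be able to answer the follow-up questions, will be asked about participation". The headache outcome is obtained "at a follow-up telephone call by a blinded nurse at the neurology outpatient clinic 5 days after LP". No rate is given for eligibility, consent or completion of the call.

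**The concern.** The number used for power is close to a count of every procedure the clinic performs. Three losses stand between an LP and an analysed patient: some people will be judged unable to answer follow-up, some will decline, and some will not be reached on day 5. The plan sets none of them against the 900. Recruitment closes on a calendar date rather than at a target number, so any shortfall reduces n instead of lengthening the study.

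At stake is the reliability of the comparison between needed and available n. One aim is to learn how much headache incidence differs between the 22G and 25G atraumatic needles. That contrast has no surplus at 900, so it absorbs any loss directly, and a non-significant result there would be less informative than the stated 80% suggests.

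**Working it through.** **1. Reproduce the plan's figures.** Inputs are the rates in the Power section, alpha 0.05 and 80% power. The plan does not state sidedness; two-sided reproduces its numbers. The pooled chi-square formula without continuity correction is

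n per group = [1.96·√(2p̄(1−p̄)) + 0.8416·√(p₁(1−p₁)+p₂(1−p₂))]² / (p₁−p₂)².

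- Size, 20% vs 12%: p̄ = 0.16; [1.96·√0.2688 + 0.8416·√0.2656]² / 0.0064 = 328.5, so 329.
- Type, 24.4% vs 12.2%: 157.
- Stylet, 16% vs 5%: 121.

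All three match the plan. One-sided (259, 124, 95) and continuity-corrected (354, 173, 139) versions do not.

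**2. Compare 900 with LP volume.** Inputs are 250–300 lab LPs plus 50 ward LPs a year (Background).

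- 3 years: (300 to 350) × 3 = 900 to 1,050. 900/1,050 = 86%; 900/900 = 100%.
- 2 years: 600 to 700. The plan's 600 (3 × 200) is again 86–100%.

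**3. Power for needle size at 20% vs 12%.** With the same formula,

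power = Φ{[0.08·√n − 1.96·√0.2688] / √0.2656} = Φ{[0.08·√n − 1.016] / 0.515}.

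| Evaluable per needle | Basis | Power |
|---|---|---|
| 300 | full 900 | Φ(0.717) = 76% |
| 270 | 10% below 900 (illustrative) | Φ(0.579) = 72% |
| 240 | 20% below 900 (illustrative) | Φ(0.433) = 67% |

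These are single-look values at two-sided 0.05, with no adjustment for the planned interim analysis or for multiple comparisons.

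**4. The other two contrasts with half of the 900 lost (illustrative).**

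- Type, 150 per needle: Φ{[0.122·√150 − 1.072] / 0.540} = Φ(0.782) = 78%. At the full 300 it is 97%.
- Stylet, 225 per option: Φ{[0.11·√225 − 0.850] / 0.4265} = Φ(1.876) = 97%. At the full 450 it is above 99.9%.

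**5. Share of all 3-year LPs that must be evaluable for 80% power.**

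- Size: 3 × 329 = 987, which is 94% of 1,050 and 110% of 900.
- Type: 3 × 157 = 471, or 45–52%.
- Stylet: 2 × 121 = 242, or 23–27%.

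**The case against.** The strongest reply is that the plan already shows the size shortfall by printing 329 beside 300, and that the gap at full enrolment is small: with 300 per needle, 80% power applies at about 20.4% vs 12%. Both points are right. The plan hides nothing here; it leaves the achieved power unstated.

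It is also fair that 20% vs 12% is the plan's own smallest difference. Its cited ranges are 5–12% and 20–40%. Taking the midpoint of the lower range, (5 + 12)/2 = 8.5%, against 20% needs 144 per group by the same formula, with 98% power at 300 and 82% at 150. So 76% applies to the least favourable size scenario, not to every plausible one. The volumes are also approximate planning figures.

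What survives is that the 80% standard is applied to this scenario, and that the n set against it assumes nearly every LP yields an analysed patient.

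Some stronger readings are tempting but unsupported:

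- **The whole trial is underpowered.** At the plan's own rates, type and stylet tolerate heavy loss (step 4).
- **900 is more than the clinic can supply.** This requires excluding ward LPs, which are done "usually on on-call time when the LP-lab is closed". Recruitment is defined by the clinic, with no restriction to the lab.
- **Needle type is also short, because the study's equal-size comparison is at 25G.** The 5–12% range is a frequency for 24–27G needles in general; nothing assigns its ends to cutting and atraumatic tips. Whether 22G rates carry over to 25G is a separate effect-size question.
- **The budget for 900 case report forms shows that enrolled and analysed numbers were equated.** The budget says nothing about the analysis set.
- **Repeat LPs in one person shrink n further.** The plan is silent on them, but that is a question of eligibility and independence, and the documents give no figure for it.

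**Conclusion.** The point holds, with a limited reach. The 900 is 86–100% of all LPs at the reported volume and carries no stated allowance for non-participation or loss, so the available group sizes in the Power section are optimistic. The practical effect is mainly on needle size at 20% vs 12%: 76% power at the plan's full 900, and 72% or 67% at 10% or 20% fewer evaluable patients. Reaching 80% there would take 94% of all LPs at the top of the volume range, and is impossible at the bottom. Type and stylet remain adequate at their cited rates.

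This rests on the Background volumes continuing through the recruitment window, an uncorrected two-sided chi-square at a single look, and loss fractions chosen only for illustration.

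**What to change.** In the Power section, replace 900 with an expected evaluable n: LP volume multiplied by an assumed participation-and-follow-up fraction, shown as a range. As an illustration of the form only, 80% of 900–1,050 LPs is 720–840 patients, or 240–280 per needle. At that n, restate the power, or the difference detectable with 80% power, for all three contrasts. For size at 20% vs 12%, give 76% at 300 per needle as the upper bound under the planned 900, labelled as a single-look value at two-sided 0.05.

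The cost is a few sentences. Design, conduct and recruitment window stay as they are, and no extra enrolment is needed. The downside is that the stated n and power become less favourable, and that the sponsor must commit to a fraction that is itself uncertain, which is why a range is preferable to a single value.

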### **Purpose and method**

The purpose of this study is to investigate how three different needles work with regard to usability, time efficiency and PLPH incidence in the clinic. The needles included are:

1. Sprotte 25G (0.5 mm) atraumatic with introducer
2. Sprotte 22G (0.7 mm) atraumatic with introducer
3. Spinocan 25G (0.5 mm) cutting

Rationale for the choices of needles: If the PLPH incidence is already low when using cutting 25G needle, and does not significantly decrease when using the same size atraumatic needle, it may be health economically reasonable to choose the former because of lower price and no need to anesthetize before insertion (the needle is not thicker than the anesthetic needle, and it is mainly penetration of the skin that feels uncomfortable). The larger (22G) atraumatic needle is included to examine the time saved (higher flow rate) when using it, and how much the PLPH incidence differs between it and the smaller one. If the PLPH incidence is very low already when using this larger needle, it can be argued not to go down further in size, as long as the time saving is large.

We also investigate whether reinserting the stylet before needle withdrawal reduces the frequency of PLPH by randomizing between reinserting it, or not, in all needle categories. Thus, there will be 6 different categories (3 needles x 2 stylet options). The patients will be randomized to either option using a computer program that block-randomizes (12 subjects/block, 2 of each needle/stylet category in each block). Randomization will occur stratified by gender, BMI above or below 25 and age over and below 50 years. This is to

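### The needle-size calculation gives the larger needle 20%, but the same paragraph gives 12.2% for a non-cutting 22G needle, so n = 329 does not describe the trial's Sprotte 22G versus 25G contrast

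*Combined protocol and SAP*

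**What the plan says.** The Purpose and method section lists three needles. Only one is 22G: "Sprotte 22G (0.7 mm) atraumatic with introducer". The other two are 25G, one atraumatic (Sprotte) and one cutting (Spinocan). The section explains that the 22G needle is there to measure the time saved and the size of the difference in PLPH from the smaller needle. The Background treats atraumatic and non-cutting as the same thing.

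The Power section sets the assumptions: "In power calculations we assume an alpha = 0.05, power = 80%, a chi-2 test to show differences between the groups, and 900 participants". It then makes three calculations, two of which bear on this point.

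- **Needle type.** "LP with a non-cutting needle (22G) gave a PLPH incidence of 12.2%, compared to cutting (22G) 24.4" (per cent), which leads to 157 per group.
- **Needle size.** "The frequency PLPH with 24–27G needle is 5–12%, and for needles in sizes 20–22G 20–40" (per cent). The nearest ends of these ranges are then used: "To detect the smallest possible difference (20% vs. 12%) we would need n = 329 patients". Beside this figure the plan prints the numbers it expects per needle, 300 after three years and 200 after two.

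The size ranges are given by gauge alone. The plan does not say which needle types they cover. It also does not comment on the fact that its own 12.2% for a non-cutting 22G needle lies below the 20–40% range.

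**The concern.** The rate assumed for the larger needle in the size calculation conflicts with the rate given for that kind of needle in the same paragraph. The 12.2% is used for needle type and then dropped for needle size without a reason. As a result, the claim that 8 percentage points is the smallest difference that could arise is true of the two cited ranges but not of the needles being randomised.

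At stake is what the plan tells its reader about one of its main contrasts. Setting 300 against 329 suggests a modest, known shortfall. If the 22G rate is nearer 12%, that comparison says little about the real power, which then depends almost entirely on a 25G atraumatic rate that the plan never states.

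**Working it through.** **Inputs.** Alpha 0.05, power 80% and a chi-square test on two proportions (Power section). The plan does not say whether the test is two-sided, but the two-sided version reproduces its figures. Rates of 20%, 12%, 12.2%, 24.4%, 16% and 5% come from the Power section, as do the 300 and 200 per needle.

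**Formulas.** Pooled-variance chi-square, equal groups, no continuity correction, with p̄ = (p₁ + p₂)/2:

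n per group = [1.960·√(2p̄(1−p̄)) + 0.842·√(p₁(1−p₁) + p₂(1−p₂))]² / (p₁ − p₂)²

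Power at n per group = Φ{[|p₁−p₂|·√n − 1.960·√(2p̄(1−p̄))] / √(p₁(1−p₁) + p₂(1−p₂))}, plus the opposite tail, which is negligible except when the two rates are close.

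**Step 1: reproduce the plan.**

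- 20% vs 12%: (1.0162 + 0.4337)² / 0.08² = 328.5, so 329.
- 24.4% vs 12.2%: 156.5, so 157.
- 16% vs 5%: 120.7, so 121.

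All three match, so the arithmetic is sound and the question is only about the input. For 20% vs 12%, power is 76% at 300 per needle and 59% at 200.

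**Step 2: put 12.2% in for the 22G arm.** The 25G atraumatic rate is an assumption. The plan's 5–12% for 24–27G is by gauge only, so the table also includes a value below it.

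| Assumed 25G rate | Difference (points) | n per needle for 80% power | Power at 300 | Power at 200 |
|---|---|---|---|---|
| 4% | 8.2 | 173 | 96% | 85% |
| 5% | 7.2 | 237 | 88% | 73% |
| 6% | 6.2 | 337 | 75% | 58% |
| 7% | 5.2 | 503 | 58% | 42% |
| 8% | 4.2 | 807 | 40% | 29% |
| 10% | 2.2 | about 3,200 | 14% | 11% |

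Worked example at 6%: (0.7972 + 0.3403)² / 0.062² = 336.6, so 337.

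**Step 3: test the claim about the smallest difference.** With 22G at 12.2%, the gap is below 8 points whenever the 25G rate exceeds 12.2 − 8 = 4.2%. Across the whole cited 5–12% range it runs from 12.2 − 5 = 7.2 points down to 12.2 − 12 = 0.2 points. So 8 points is not a lower bound for this contrast.

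**Step 4: find where 80% power is reached.** Solving the power formula for the 25G rate with 22G fixed at 12.2% gives about 5.7% at 300 per needle and about 4.5% at 200.

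**The case against.** Several points on the other side are sound.

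- **The 25G rate is not known either.** It would be inconsistent to reject a gauge-only range for 22G and then treat the gauge-only 5–12% as the rate for the atraumatic 25G needle. The Background says non-cutting needles carry less risk than cutting ones of the same size, and the Power section shows a halving at 22G. If the 5–12% came from cutting needles and the same halving held (both assumptions), atraumatic 25G would be at 2.5–6%. Power at 300 would then be above 99% at the low end and 75% at the high end. Halving both nearest ends instead, to 10% vs 6%, needs 721 per needle and gives 44% power. The documents do not settle this. The objection stands, and it is why the result has to be shown as a range.
- **A smaller gap does not always need more patients.** At 12.2% vs 5% the gap is below 8 points, yet 237 suffice, because the variance is lower at lower rates. This also stands.
- **The phrase follows from the two ranges.** As the distance between their nearest ends, 8 points is correct. That defends the sentence as a summary of the cited source, but not as a description of the trial's needles.
- **The shortfall is already disclosed.** The plan prints 300 beside 329 and does not claim 80% power for size. That is so, but the disclosure concerns the number of patients available. It does not tell the reader that the assumed rates may not apply.

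A reader might also infer that a non-significant 22G versus 25G result would be used to argue for the larger needle. The documents do not support this. The Purpose and method section ties the case for 22G to a very low PLPH incidence with that needle together with a large time saving. Its wording about a non-significant decrease concerns cutting versus atraumatic 25G, which is a different contrast.

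**Conclusion.** The point holds as a mismatch of inputs. The size calculation uses 20% for a needle whose kind is given 12.2% in the same paragraph, so 329, and the 76% power it implies at 300, do not describe Sprotte 22G versus Sprotte 25G. If 22G is at 12.2%, 329 is about right only when the 25G rate is close to 6%. Below that fewer patients are needed, and above it the number rises steeply.

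A reader might infer that the trial is simply underpowered for needle size. The documents do not show that. Power at 300 per needle runs from 96% to 14% as the assumed 25G rate goes from 4% to 10%, and the plan gives no figure that picks out one value. The conclusion rests on taking the single cited 12.2% as the 22G rate, on a two-sided test at 0.05, and on equal groups of 300 (or 200 at two years).

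**What to change.** In the Power section, replace the 20% vs 12% sentence with a calculation for the trial's own contrast: 12.2% for 22G atraumatic against a stated range of rates for 25G atraumatic. Alternatively, explain why 20% applies to a non-cutting 22G needle. Remove the claim that this is the smallest difference possible. State that, if 22G is at 12.2%, 80% power requires a 25G rate of about 5.7% or lower with 300 per needle and about 4.5% or lower with 200.

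Report the 22G versus 25G result as a risk difference with a 95% confidence interval. This suits the stated aim, which is to learn the size of the difference.

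The cost is a few reworded sentences, with no extra patients and no change to the design. The downside is that the stated power becomes less certain and possibly less favourable.
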